#### Inclusion and exclusion criteria

This study will include adult pregnant women regardless of age. Pregnant minors under the age of 18 will not be eligible.

A patient will be considered for inclusion in the study if she meets all of the following criteria:

- She has a term (≥37 completed weeks) live singleton gestation in cephalic presentation and has been admitted to the Labor and Delivery Unit
- She is in the latent phase of labor or has been admitted for induction of labor or at prenatal clinic visit
- She has had fewer than four prior vaginal deliveries.
- She reports no allergy to misoprostol.

The following factors or conditions will exclude a patient from consideration as a subject:

- The fetus has a known major fetal malformation or chromosome abnormality
- The gestation is multiple.
- There is a breech or other malpresentation
- The patient reports involvement in another clinical trial currently or previously in this pregnancy.
- The patient is expected to have a cesarean delivery.
- The patient had a prior cesarean delivery.
- There has been an intrauterine fetal death.
- There is polyhydramnios (amniotic fluid index >22 cm).
- Presence of acute or chronic renal disease
- Presence of preeclampsia

Of subjects who enter the study, the development of certain conditions will exclude them post hoc from receiving misoprostol under the protocol, and from the data analysis. These conditions include:

- Unanticipated cesarean delivery.
- Performance of episiotomy (third and fourth degree extensions will be excluded).
- Vaginal or cervical laceration, or perineal laceration of more than second degree in depth.
- Severe postpartum hemorrhage requiring intervention immediately after delivery.
- Uterine rupture
- Placental abruption.
- Patient withdrawal of consent.

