#### Abstract

This document defines the Clinical Investigation Protocol for a study designed to determine whether blood loss after spontaneous vaginal delivery is altered by the addition of misoprostol administration to the standard use of intravenous oxytocin after delivery. The protocol is an open-label randomized prospective trial to be carried out at Queens Hospital Center.

Blood loss will be measured indirectly by comparing the maternal hemoglobin and hematocrit levels on admission in labor to those obtained within 24 hours after delivery.

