## Background

Some maternal blood loss normally occurs at the time of vaginal delivery. The best estimates indicate that a loss of approximately 500 mL is average, with a range of about 250-700 mL.[1,2] Some of this bleeding arises from birth canal lacerations or surgical incisions (i.e., episiotomy), but most derives from the vessels exposed in the uterine wall at the placental site once the placenta has separated.

Under normal circumstances, shortly after placental separation intense myometrial contractions occur. These raise the pressure within the myometrial wall above that of the blood pressure in the vessels that traverse it, vessels that opened into the intervillous space. Flow in these vessels is thus mechanically attenuated by myometrial contraction, allowing for the formation of intravascular thrombi.

This mechanism for controlling postpartum uterine blood loss works well most of the time. If, however, the uterus remains hypotonic or atonic after delivery, excessive blood loss can occur. In the worst cases, severe uterine hemorrhage ensues. Postpartum hemorrhage is, in fact, the leading cause of maternal mortality in the world, accounting for at least 100,000 deaths annually.[3] Even in the absence of frank hemorrhage, postpartum blood loss can result in maternal anemia. Recuperation of iron stores to recover from this blood loss takes time, and may not occur, especially in low socioeconomic areas where dietary iron consumption is often deficient, and pregnancies tend to occur in close succession.

Postpartum anemia is a significant contributor to short- and long-term morbidity.[5-7] It increases the risk of infection and poor wound healing. Also, the associated fatigue may interfere with the mother's ability to administer child care and to bond appropriately with her infant. Anemic mothers tend to have more difficulty with nursing, and may produce iron-deficient milk. There is thus a strong rationale to minimize postpartum blood loss.

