## **Preliminary Data**

We examined the hemograms of a randomly chosen consecutive sample of 53 spontaneous vaginal deliveries performed at Queens Hospital Center between September 15 and October 1, 2010.

Among these patients, the admission hemoglobin concentration was 11.9±1.2 g/dL and that on the first postparutum day was 10.9±1.3. The mean fall was 1.02 (95% CI 0.74, 1.29), a statistically significant decrease (P<0.0001). Hematocrit levels fell in parallel, by an average of 7.8% of the predelivery value. The mean fall in hemoglobin and hematocrit levels after delivery (1.02 g/dL and 2.81%) is consistent with an average blood loss of about 500 mL. The consistency of these changes and the small associated variance indicate that the change in hemoglobin and hematocrit levels is a meaningful proxy for the assessment of blood lost during vaginal delivery.

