# Study Procedure

Informed consent will be obtained by one of the investigators or informed consent delegates. The subject will then be assigned randomly to the control (oxytocin alone) or the study (oxytocin + misoprostol) group, as described above. The subject and her medical caretakers will be informed of which group she is in. If the labor eventuates in a vaginal delivery, all subjects will receive the standard dose of intravenous oxytocin, begun within one minute of delivery. Subjects in the study group who have not incurred any of the post-hoc exclusion criteria (episiotomy, major laceration, etc) will receive a dose of 600 µg of misoprostol in addition to their oxytocin. This will be administered in the form of six 100 µg tablets inserted approximately 2 cm into the anorectal canal by the obstetrician or midwife who has performed the delivery. The common method for administering Misoprostol for postpartum hemorrhaging is rectally for local absorption. Since this study is directed toward prevention instead of treatment, the dosage of 600mg is a lower dosage from the 1000mg administered, as standard practices, for treating postpartum hemorrhaging of more than 500cc estimated blood loss. patient's vital signs will be recorded after delivery according to standard protocols of the obstetric service. The Data Collection forms will be filled out after the delivery by one of the investigators. The measurement of postpartum hemoglobin and hematocrit (H & H) is automatically ordered at 06:00am for all patients who have delivered the day prior, constituting this measurement at "Postpartum Day 1", which is at a minimum of 6 hours after delivery and is enough time for H & H levels to stabilize.

Within 36 hours of delivery, additional information will be collected from the patient's record, including the postpartum hemogram and information about any symptoms or signs related to the misoprostol.

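### Randomised women are dropped from the only analysis for events after assignment, including severe hemorrhage, in an open-label trial with no analysis by assigned group

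*Combined protocol and SAP*

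**What the plan says.** All references are to the combined protocol and SAP.

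- *Recruitment and Consent Procedures* and *Study Procedure*: consent comes before active labor, and randomisation follows consent.
- *Study Procedure*: "The subject and her medical caretakers will be informed of which group she is in".
- *Inclusion and exclusion criteria*: for women already in the study, "the development of certain conditions will exclude them post hoc from receiving misoprostol under the protocol, and from the data analysis". The list is unanticipated cesarean, episiotomy, certain lacerations, "Severe postpartum hemorrhage requiring intervention immediately after delivery", uterine rupture, abruption and withdrawal of consent.
- *Study Procedure*: the drug goes to "Subjects in the study group who have not incurred any of the post-hoc exclusion criteria".
- *Sample size and analysis*: the only test named is a paired t-test of intrapartum against postpartum values. The 800 women carry no allowance for exclusions.
- *Study Design*: the groups are described by treatment received. No section plans a comparison by assigned group, a sensitivity analysis, or reporting of exclusions by arm.

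**The concern.** One sentence makes two separate decisions: who is not given misoprostol, and who is not analysed. The first is a treatment rule and is not questioned here. The second removes randomised women because of what happened after assignment.

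Two kinds of exclusion matter most. Severe hemorrhage is the tail of the quantity being measured, so removing it trims the outcome itself. Laceration grade, episiotomy and the word severe call for judgement, by staff who know the group. If the two arms are trimmed differently, the hemoglobin comparison shifts without any drug effect.

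Because the restricted set is the only analysis, a reader could count most exclusions by arm from the *After Delivery* data list but could not see whether the result depends on them. Hemorrhage requiring intervention, its time, uterine rupture and actual receipt of misoprostol are not on that list.

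**Working it through.** **1. The plan's own figure.** Inputs from *Sample size and analysis*: difference 0.3 g/dL, SD 1.3, two-sided 0.05, power 90%. An equal split of 400 per arm is assumed.
- n per arm = 2 × (1.960 + 1.282)² × 1.3² / 0.3² = 395, or 790 in total, against 800 stated.
- Power at 400 per arm: 0.3 / (1.3 × √(2/400)) = 3.264, and Φ(3.264 − 1.960) = 90.4%.

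The stated 90% reproduces, provided that all 800 are analysed.

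**2. SD of the fall.** *Preliminary Data* gives a mean fall of 1.02 (95% CI 0.74 to 1.29) in 53 women, and SDs of 1.2 and 1.3.
- Half-width (1.29 − 0.74)/2 = 0.275; SD = 0.275 / 2.007 × √53 = 0.998, taken as 1.00.
- Implied correlation of admission and day 1 values: (1.2² + 1.3² − 0.998²) / (2 × 1.2 × 1.3) = 0.684.
- SD after adjustment for admission hemoglobin: 1.3 × √(1 − 0.684²) = 0.948.

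**3. Exclusions before dosing, alike in both arms.** Bias is zero. If 20% are excluded (assumed), 320 per arm remain. Power for 0.30 g/dL falls from 90% to 83% at SD 1.3, and from 98.9% to 96.7% on the fall.

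**4. Uneven exclusion of the worst cases, no true effect.** The rates are assumed. The test is a two-sample comparison of falls, which the plan does not name. Let ρ be the correlation between the tendency to be excluded and the hemoglobin fall. Removing the top fraction p lowers the mean fall of those kept by ρ × SD × λ, where λ = φ(z)/(1 − p) and z is the upper-p normal point. Their variance becomes SD² × [1 − ρ²(zλ + λ²)].
- p = 5%: λ = 0.1031/0.95 = 0.1086. p = 2%: λ = 0.0484/0.98 = 0.0494.
- Bias at ρ = 1: 0.998 × (0.1086 − 0.0494) = 0.059 g/dL. At ρ = 0.5: 0.030.
- Standard error at ρ = 1: 0.998 × √(0.810/380 + 0.896/392) = 0.066. The ratio is 0.89, and Φ(0.89 − 1.96) + Φ(−0.89 − 1.96) = 14%.

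| Excluded, one arm against the other | Bias, g/dL (ρ = 1 / 0.5) | Type I error (ρ = 1 / 0.5) |
|---|---|---|
| 5% against 4% | 0.019 / 0.009 | 6% / 5% |
| 5% against 3% | 0.038 / 0.019 | 9% / 6% |
| 5% against 2% | 0.059 / 0.030 | 14% / 7% |

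In 20,000 simulated trials at 5% against 2%, the restricted set rejected in 14.3% / 6.7%. The same trials analysed by assigned group rejected in 5.1% / 5.0%. The bias favors whichever arm loses more of its worst cases.

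**5. Price of analysing by assigned group.** If 20% of the study arm is untreated (assumed) and gains nothing, the effect is 0.30 × 0.80 = 0.24 g/dL.

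| Power for 0.24 g/dL | SD 1.3 | Fall, SD 1.00 | Adjusted, SD 0.948 |
|---|---|---|---|
| 400 per arm | 74% | 92% | 95% |
| 320 per arm | 65% | 86% | 89% |

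**The case against.** The strongest reply is that the restriction is deliberate and harmless. *Background* separates bleeding from lacerations and episiotomy from placental-site bleeding, and *Characteristics of Medication* says that misoprostol acts on the myometrium. Women without major trauma are therefore a reasonable target group. The rule covers both arms. Cesarean, episiotomy, rupture and abruption cannot result from a drug given after delivery. That all stands, and it supports keeping the restricted set as a secondary analysis. It does not support making that set the only one.

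Three stronger readings are tempting, and the documents do not support them.

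- *That study-arm women are dropped for hemorrhage after misoprostol.* The exclusion is worded as arising straight after delivery, it is also a reason to withhold the drug, and the drug goes only to women with no exclusion. Read together, these put study-arm exclusions before dosing. What remains open is the end of the window in controls, who have no dosing moment.
- *That average blood loss would lead to exclusion.* *Study Procedure* mentions a dose "for treating postpartum hemorrhaging of more than 500cc estimated blood loss", and *Background* says that "a loss of approximately 500 mL is average, with a range of about 250-700 mL". But the first figure describes standard treatment, and the protocol never equates it with severe hemorrhage. Severe is undefined, so no exclusion rate can be derived.
- *That the result will be biased.* Nothing suggests that staff will apply the rule unevenly. At ρ = 0.5, every scenario above gives a type I error of 5% to 7%.

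The episiotomy item is also ambiguous. Its parenthesis on third and fourth degree extensions may limit the exclusion to those cases, whereas *Study Procedure* lists episiotomy without that limit. The two places must be reconciled.

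**Conclusion.** The point holds as an omission in the analysis plan: exclusions after randomisation, one of them the extreme of the outcome, with the group known and no analysis by assigned group. Confidence is high on the omission and low on the size of any harm.

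Bias needs either uneven judgement by unblinded staff or a hemorrhage window that runs differently in controls. With an assumed 5% against 2% exclusion of the worst cases it is 0.03 to 0.06 g/dL, a tenth to a fifth of the 0.3 g/dL target, with type I error of 7% to 14%. At 5% against 4% it is close to nothing. These figures rest on assumed rates, normal falls with SD 1.00, and a two-sample test of falls. They are not error rates of the paired t-test that the plan names. The sample size arithmetic is not at fault.

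**What to change.** Leave the rule on who receives misoprostol unchanged. Limit removal from the data analysis to withdrawal of consent, handled as the consent allows, and, for the primary analysis only, cesarean. Leaving cesarean out fits the stated question, whether "blood loss after spontaneous vaginal delivery is altered by the addition of misoprostol administration". Add:

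> The primary analysis compares hemoglobin change between arms by assigned group in all randomised women who deliver vaginally, have not withdrawn consent for use of their data, and have admission and day 1 hemoglobin, whether or not misoprostol was given.

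Then:

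- Keep the present restricted set as a sensitivity analysis, and add one that includes cesareans.
- For analysis only, define severe hemorrhage requiring intervention with one time window in both arms.
- Report exclusion events, withdrawals, transfusion, misoprostol receipt and missing day 1 values by arm.
- Compare falls, or adjust for admission hemoglobin, and restate the power on that basis.

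**Cost.** Protocol wording and four form items: hemorrhage requiring intervention, its time, uterine rupture, and misoprostol receipt in both arms. Hemoglobin, estimated blood loss, transfusion, cesarean, episiotomy, laceration and abruption are already collected.

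The real price is dilution. For 0.24 g/dL at 90% power, SD 1.3 needs 617 per arm (1,234 in total). On the fall, 2 × (1.960 + 1.282)² × 1.00² / 0.24² = 365 per arm. So 800 women suffice on the fall if no more than 35 of 400 per arm (about 9%) are lost to cesarean, withdrawal or missing values. Controls given misoprostol as treatment would dilute further: at an assumed 5% with the same benefit, the effect is 0.30 × (0.80 − 0.05) = 0.225 g/dL, and power on the fall at 400 per arm is 89%.

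Transfusion can also raise day 1 hemoglobin. If 2% of controls and 1% of the study arm are transfused, with a rise of 1 to 2 g/dL (all assumed), the difference moves by (0.02 − 0.01) × 1 to 2 = 0.01 to 0.02 g/dL against a benefit.

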#### Recruitment and Consent Procedures

Patients who meet the inclusion criteria for the study will be identified during their prenatal clinical visits, in early latent-labor, or prior to induction of labor or active labor. Informed consent will be obtained by one of the investigators. Consent will be obtained prior to active labor. The informed consenting process will not be initiated among patients in active labor. Patients will be recruited and consented with the consent document approved by the IRB. Patient recruitment will commence after IRB approval is obtained.

Once the subject has consented to participate in the study, it will be determined by the investigator whether the patient will receive oxytocin alone or oxytocin and misoprostol. Both drugs are on formulary and will be available on the Labor and Delivery Unit for immediate use.

#### Randomization

A computer-generated table of random numbers will be used to assign the recruited subject to a group. A locked file will be maintained in the Labor and Delivery area. The file will contain a series of sequentially-numbered sealed envelopes. Each envelope will contain a card with a randomly generated number. These numbers will have been taken in order from the computer-generated list. The investigator will choose the next envelope in sequence. If it contains an odd number, the patient will be assigned to the intervention group and will receive oxytocin and misoprostol. If the envelope contains an even number, the patient will be assigned to "oxytocin only" group.

#### Characteristics of Medication

#### Nature of misoprostol

Misoprostol is a synthetic prostaglandin E1 analog. It is marketed primarily as a drug to prevent the development of gastric ulcers associated with use of nonsteroidal anti-inflammatory drugs, and is part of the Queens Hospital Center formulary. Originally marketed as Cytotec®, misoprostol is available in a generic form as tablets containing contain either 100 µg or 200 µg. Misoprostol protects the gastric mucosa through several mechanisms. It also has the property of stimulating myometrial smooth muscle contraction.[12] That effect has resulted in the drug's common use in obstetrics for termination of pregnancy, cervical ripening prior to induction of labor and, in large doses, for prevention and treatment of postpartum hemorrhage from uterine atony. [13-19]

Misoprostol can be administered by oral, sublingual, vaginal or rectal routes. It is well absorbed with all these modes of administration, but detailed pharmacokinetic data exist primarily concerning its oral administration. It is rapidly absorbed, and undergoes prompt de-esterification to its free acid, which is responsible for its clinical activity. Peak plasma levels after oral administration occur after 10-15 min. The half-life is 20-40 minutes. The alpha side chain undergoes beta oxidation and the beta side chain undergoes omega oxidation followed by reduction of the ketone to give prostaglandin F analogs. Excretion is primarily in the urine.

Very little misoprostol appears in breast milk. [20,21] After a single 600  $\mu$ g oral dose of misoprostol to nursing mothers, misoprostol acid was excreted in breast milk. One hour after dosing, the milk concentration was about 67% of the maternal serum level; by five hours, the misoprostol concentrations in breast milk declined to < 1 pg/mL. While no specific data exist for misoprostol concentrations in colostrum, given the very small ingested volume over the first few hours of life, neonatal exposure to the drug in our study can be expected to be minimal. There are no published reports of adverse effects of misoprostol in breast-feeding infants of mothers taking misoprostol

Misoprostol is classified by the FDA as a Pregnancy Category X drug. This label is related to its possible association with congenital anomalies when used in the first trimester, as well as its abortifacient properties. In our study, patients will no longer be pregnant when they receive the drug.

The use of misoprostol to enhance uterine activity postpartum is an off-label method, but one that has gained wide acceptance, and for which there is considerable experience.[8-10, 12-19] The drug can cause nausea, headache, dyspepsia, vomiting, and constipation or diarrhea with multiple doses. These side effects are usually mild to moderate and generally subside within a week. Serious side effects after a single dose are quite rare. In one study of 327 women who received 600 µg rectally (the dose we propose to use), the most common side effects were transient shivering (26%) and pyrexia (15%). Both were mild and short-lived. [16]

# Benefits and Risks to Study Subjects

There will be no certain medical benefit to the subjects who participate in the study. It is possible that they will benefit from reduced postpartum blood loss.

Risks to the subjects are those associated with administration or misoprostol.

These include the following adverse events that have been reported in subjects receiving misoprostol for ulcer prophylaxis: diarrhea, abdominal pain, nausea, flatulence, headache, dyspepsia, vomiting, and constipation. All occurred in fewer than 5% of patients. Other reported effects that occurred in clinical trials of misoprostol, but for which no cause-effect relation has been established included fatigue, fever, chills, rash, alopecia, pallor, breast pain, abnormal taste, abnormal vision, conjunctivitis,

deafness, tinnitus, earache, chest pain, edema, diaphoresis, hypotension, hypertension, arrhythmia, phlebitis, increased cardiac enzymes, syncope, myocardial infarction, thromboembolism, abnormal hepatobiliary function, gingivitis, reflux, dysphagia, gout, polyuria, dysuria, hematuria, urinary tract infection, anxiety, depression, and thrombocytopenia. As with any drug, anaphylaxis is possible.

We emphasize that in a number of published studies using a single postpartum dose of misoprostol of  $600-1000~\mu g$  and including in aggregate in excess of 1000~patients, no serious side effect has been reported.

Side effects after a single dose of misoprostol are rare. Misoprostol can cause nausea, headache, heartburn, vomiting, flatulence, and constipation or diarrhea with multiple doses. These side effects are usually mild to moderate and generally go away within a week. Mild shivering and slight fever are the most likely side effect of this medication. If they occur, they will probably disappear within an hour.

Oxytocin commonly causes vomiting and nausea. Oxytocin has the potential to cause muscle contractions. In rare cases, Oxytocin can cause heart palpitations (rapid heartbeat) and allergic reaction of a rash or swelling.

It is unknown whether Misoprostol and/or Oytocin are excreted in human milk. There is an unconfirmed relation with Misoprostol and/or Oytocin causing digestive problems, such as diarrhea, and abdominal cramps in breast-fed newborns. Pariticipants will be advised to discard breast mild for the first 24 hours to possibly avoid occurrence.

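### The risk section calls single-dose side effects rare against the protocol's own 26% shivering and 15% fever, and the attribution wording for harms collection conflicts with the data list and invites unequal recording between arms

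*Combined protocol and SAP*

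**What the plan says.** All references are to the combined protocol and SAP.

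**Frequency of side effects.** Benefits and Risks to Study Subjects says: "Side effects after a single dose of misoprostol are rare". Nature of misoprostol makes a narrower claim: "Serious side effects after a single dose are quite rare". It supports this with a cited study at the planned 600 µg rectal dose ("In one study of 327 women who received" it), which gives 26% for shivering and 15% for pyrexia and adds: "Both were mild and short-lived".

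**Disclosure and causality.** Three sentences after the *rare* statement, the risk section says: "Mild shivering and slight fever are the most likely side effect of this medication". It attaches no rate. Earlier, the same section lists other effects seen in misoprostol trials, "for which no cause-effect relation has been established included fatigue, fever, chills" among them. Its only percentage for misoprostol effects is a figure of fewer than 5%, for events reported under ulcer prophylaxis.

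**Collection of harms.** Study Procedure has further data taken from the patient's record within 36 hours of delivery, including "information about any symptoms or signs related to the misoprostol". It also has vital signs recorded after delivery under the service's usual practice. The list under Results – includes Follow-up Data contains patient-reported side effects, temperature after delivery and reported shivering, none of them limited by arm or cause. Study Procedure makes group membership known to the woman and her caretakers.

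**Analysis.** Sample size and analysis deals only with hemoglobin and hematocrit. No comparison of harms between arms is described.

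**The concern.** There are two linked faults.

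First, the risk section drops the word *serious* and so turns a defensible statement into one that the protocol's own evidence contradicts. An effect seen in about one woman in four is not rare, even if it is mild and brief. The causality list adds to the confusion: fever and chills appear as effects with no established link to the drug, yet shivering and fever are then named as its likeliest side effects. Anyone relying on this section alone, such as an ethics committee or whoever drafts the consent text, would get the wrong idea of frequency.

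Second, a collection rule based on relatedness to misoprostol has no meaning for women who receive none. Shivering and raised temperature after delivery can have other causes, and the trial needs the background rate counted on the same basis in both arms. With treatment known to everyone and shivering captured through reports, the attribution wording could lead staff to record it more readily in the misoprostol arm. The benefit sought is a difference of 0.3 g/dL in hemoglobin, and the excess of shivering and fever is what it must be weighed against. That excess should not depend on who thought to write it down.

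**Working it through.** **1. The plan's own calculation.** Inputs from Sample size and analysis: difference 0.3 g/dL, SD 1.3 g/dL, two-sided 0.05, 90% power, 800 women. Per arm, n = 2 × (1.96 + 1.2816)² × 1.3² / 0.3² = 394.6, so 395 per arm and 790 in total. With 400 per arm the power is 90.4%. The plan's figure reproduces and is not in dispute. It is used here only for the arm size of about 400, which assumes an even split; the odd/even assignment implies this but no ratio is stated.

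**2. Can sampling error rescue *rare*?** Inputs from Nature of misoprostol: 26% and 15% of 327 women.
- Shivering: 0.26 × 327 ≈ 85 women; exact (Clopper-Pearson) 95% CI 21.3% to 31.1%.
- Pyrexia: 0.15 × 327 ≈ 49 women; exact 95% CI 11.3% to 19.3%.

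Both lower limits lie well above the 5% ceiling that the risk section quotes for ulcer-prophylaxis effects.

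**3. Expected numbers in this trial.** If 400 women received misoprostol, 400 × 0.26 = 104 would shiver and 400 × 0.15 = 60 would have fever. Fewer will be dosed, because Inclusion and exclusion criteria withholds misoprostol after unplanned cesarean, episiotomy and other events.

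**4. The two collection texts side by side.** Study Procedure: symptoms or signs attributed to misoprostol, from the record. Data list: patient-reported side effects, temperature and shivering, with no attribution. Read literally, a control woman who shivers is recorded under the second text and not under the first. Neither text gives a common question, an assessment time or a definition of fever.

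**5. What equal collection would deliver.** The documents give no control rates, so the values below are assumptions shown as a range. The half-width is 1.96 × √[p₁(1−p₁)/n + p₀(1−p₀)/n].

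| Harm | Misoprostol | Assumed control | Difference | Half-width, n = 400 | Half-width, n = 200 |
|---|---|---|---|---|---|
| Shivering | 26% | 5% | 21 points | 4.8 | 6.8 |
| Shivering | 26% | 10% | 16 points | 5.2 | 7.4 |
| Shivering | 26% | 15% | 11 points | 5.5 | 7.8 |
| Fever | 15% | 5% | 10 points | 4.1 | 5.8 |
| Fever | 15% | 10% | 5 points | 4.6 | 6.5 |

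For example, shivering 26% v 10%: 1.96 × √[(0.1924 + 0.0900)/400] = 0.052. The n = 200 column illustrates the effect of post-hoc exclusions; it is not a forecast.

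Power at 400 per arm is above 99% for shivering 26% v 5%, 97% for 26% v 15%, and 99.7% for fever 15% v 5%. It is only 57% for fever 15% v 10%. At 200 per arm it is 78% for shivering 26% v 15% and 92% for fever 15% v 5%.

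**The case against.** The best defence is that the protocol discloses more than the *rare* sentence suggests. The risk section itself names mild shivering and slight fever as the likeliest effects and says they should pass quickly, and the rates stand elsewhere in the same document. This is true and softens the point. But it is disclosure without frequency, and coming after *rare* it can be read as naming the commonest of a set of uncommon events.

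The causality list can be read as general background from misoprostol trials rather than a statement about one rectal dose after delivery. That reading is possible. The section does not say so, however, and its two statements on fever still need reconciling.

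On collection, a reader might infer from Study Procedure that harms are gathered only when attributed to misoprostol, so that the excess risk cannot be measured. The documents do not support this. The Study Procedure phrase is introduced as an example of additional information, not as the full definition of harms data. The data list carries side effects, temperature and shivering with no restriction, and also chorioamnionitis, a competing cause of fever. Vital signs are recorded without limit by arm. What stands is a conflict between two texts and a risk of uneven recording.

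A reader might also infer that participants are told a common effect is rare. The consent pages are not in the review copy, so this cannot be shown either way.

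Finally, the half-widths describe what equal collection would achieve. They do not measure any bias from the present wording.

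**Conclusion.** The risk statement should be corrected. On the protocol's own evidence, shivering (26%, 95% CI 21% to 31%) and fever (15%, 95% CI 11% to 19%) are common at the planned dose and route, and *rare* fits only serious effects. This conclusion needs no outside assumption beyond taking the cited study as the protocol presents it.

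The collection point is narrower. The attribution wording in Study Procedure conflicts with the data list and, with open-label care and report-based shivering, could bias the comparison of harms between arms. The size of that bias cannot be worked out from the documents. The excess risk is measurable: under the assumed control rates and up to 400 per arm, half-widths are about 4 to 6 points, widening as the post-hoc exclusions reduce the numbers. A small excess of fever would be the hardest to establish.

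Neither fault affects the primary hemoglobin comparison.

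**What to change.** - **Benefits and Risks to Study Subjects:** limit *rare* to serious effects, give the 26% and 15% figures with their source and the note that both were mild and short-lived, and reconcile the list of effects without an established causal link with those figures. Check that the consent text agrees.
- **Study Procedure:** replace the restriction to misoprostol-related symptoms with collection of the items on the data list (shivering, postpartum temperature and listed symptoms) in both arms, with the same questions, regardless of presumed cause. State when they are assessed and how fever is defined for the analysis.
- **Sample size and analysis:** add risk differences between arms, with 95% confidence intervals, for shivering, fever and the listed symptoms.

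The cost is small. Temperature, shivering and patient-reported side effects are already to be collected, so the changes are wording, uniform questions and a short additional analysis. The downside is a less favourable risk statement.
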